- ② Secondary objectives: To explore the improvement of cardioembolic stroke, cardiovascular complex events, recurrent stroke and all-cause death risk, quality of life, and cardiac function in the "multidisciplinary assisted diagnosis and treatment mode" group and the "routine diagnosis and treatment model group". The conventional diagnosis and treatment mode can match the patients not adopted in the same period and "multidisciplinary assistance in diagnosis and treatment mode".

Design type: A non-intervention, prospective, observational, real-world study (at least 1.5 years). No fixed diagnosis and treatment plan is set up in advance, and only a multidisciplinary assisted diagnosis and treatment mode is established. All treatment options are completely made by the clinicians who follow the expert consensus of relevant textbooks and clinical guidelines, and they are formulated according to the patients' conditions.

Study subjects: Collect high-risk patients from the Second Affiliated Hospital of Nanchang University and various hospitals of Jiangxi Province from September 2022 to September 2023.

Selection criteria: ① met the high embolic risk (including intracardiac thrombosis, intracardiac tumor, aortic atherosclerosis, atrial fibrillation, and spontaneous development of ultrasound) in the risk stratification criteria of The Chinese Expert Consensus on Cardiac stroke Diagnosis (2020); ② meets the surgical indications for cardiac diseases related to the Chinese Expert Consensus on the Treatment of Cardioembolic Stroke (2022) (including left atrial fibrillation occlusion, left atrial fibrillation ligation, and radiofrequency ablation of atrial fibrillation recommended for high-risk stroke patients with atrial fibrillation; Transcatheter PFO occlusion is recommended for cryptogenic stroke patients with high-risk PFO; Valvular repair or replacement, etc.); ③ understood and voluntarily signed the informed consent form.

Exclusion criteria: ① with severe mental disorder and unable to express intention; ② with other abnormal signs, laboratory tests and clinical diseases, not suitable to attend investigator; ③ and unable to complete long-term follow-up.

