Multidisciplinary assisted care model group: Patients who agreed to and accepted the recommendation of multidisciplinary assisted care mode were enrolled in the multidisciplinary assisted care model group. These patients would undergo further stroke (primary/secondary) prevention intervention, as detailed in the MDT flow chart;

Any of the following treatments (including but not limited to), as recommended by the standard medical procedure, shall be deemed to have received the standard medical treatment; otherwise, they were not.

- 1) Surgical procedures: left atrial appendage ligation, left atrial appendage clip, valve repair or replacement, etc.
- 2) Medical procedures: atrial fibrillation radiofrequency ablation, valvular closure, left atrial appendage closure, PFO closure, etc.
- 3) Anticoagulant drug therapy: standardized anticoagulant drug therapy.

Routine treatment model group: Patients who did not agree to enter the multidisciplinary treatment mode were automatically entered into the routine treatment mode group.

Study end points:

Primary end point: Composite end point of cardiovascular and cerebrovascular events (nonfatal ischemic stroke, Nonfatal hemorrhagic stroke, Nonfatal myocardial infarction, Nonfatal heart failure, and cardiovascular and cerebrovascular death)

Secondary end points: cardiovascular and cerebrovascular death; All-cause death; Cardiac insufficiency; Cognitive dysfunction

[figure not shown]

Figure 1 Flowchart of the project

3. Research background data

1. Project approval basis

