9. Heart Rhythmology professional Committee of Chinese Medical Association, Heart Electrophysiology and Pacing Branch of Chinese Medical Association. Guidelines for the Prevention and Treatment of Cardioembolic Stroke in China (2019). *The Chinese Journal of Arrhythmia.* 2019,(06):463-484.

4. Research purpose

1. Research purpose:

Establish multidisciplinary collaboration diagnosis and treatment mode, standardize the diagnosis and treatment process: through the integration of neurosurgery, cardiac vascular surgery, neurology, cardiovascular medicine and other related disciplines, build "heart and brain treatment" multidisciplinary close cooperation system, standardize integration process and diagnosis and treatment, at the same time actively innovation relying on the relevant academic society construction, earnestly implement the multidisciplinary collaboration diagnosis and treatment mode. Based on the Internet + 5G medical model technology system and information platform, research to establish coverage relying on the remote medical service platform, the provincial, city and county center of information classification management system, by perfecting the regional collaborative emergency medical platform, improve the province cardiovascular disease acute critical patients overall treatment level, contribute to the standardization of cardiovascular stroke high-risk patients diagnosis and treatment and management. Patients with difficult and acute and critical cardiovascular and cerebrovascular diseases in the stable rehabilitation period after emergency treatment were transferred back to the primary hospital for rehabilitation, follow-up and chronic disease management and treatment.

2. Study observation endpoint

(1) Main observation endpoint: composite end point of cardiovascular and cerebrovascular events (non-fatal ischemic stroke, non-fatal hemorrhagic stroke, non-fatal myocardial infarction, non-fatal heart failure, cardiovascular and cerebrovascular death)

(2) secondary observation endpoint: cardiovascular and cerebrovascular death; all-cause death; cardiac insufficiency; cognitive dysfunction

5. Study design

1. Study site and study population

Collect high-risk patients from the Second Affiliated Hospital of Nanchang University and various hospitals of Jiangxi Province from September 2022 to September 2023.

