3. Serious adverse events: Major adverse events may be drug-related, including but not limited to the following:
 - (a) Abnormal laboratory indicators (including liver and kidney function, etc.);
 - (b) Allergic reaction to antiplatelet drugs / anticoagulants;
 - (c) Stroke / transient ischemic attack or neurological deficit;
 - (d) Spontaneous bleeding: such as petechia, ecchymosis, digestive system and urinary system bleeding;
 - (e) Central nervous system damage.
4. Assessment of the severity level
Light: do not affect the daily activities;
In: affect daily activities;
Heavy: loss of daily activity ability.

7. Data collection and management

1. Survey content (CRF table)

variable:

- a) Basic information of patients: name, gender, age, education level, combined diseases, past medical history, etc.;
- b) Admission status: chief complaints of symptoms, general condition, vital signs, CHA2DS2-VASc score, nutrition questionnaire and epidemiological data etc.;
- c) Pre-treatment laboratory and instrument examination: biochemical indicators, nutrient index (one carbon unit substance), electrocardiogram, dynamic electrocardiogram, cardiac color doppler ultrasound, foaming test, cardiac CTA, craniocerebral CT and MRI, internal and external intracranial artery evaluation, etc.;
- d) Treatment medication; surgical conditions
- e) The occurrence of adverse events during the hospitalization period;
- f) Situation at follow-up: chief complaint of symptoms, general condition, vital signs, Quality of Life, HAS-BLED score, etc.;
- g) Laboratory and instrumental examination at follow-up: biochemical indicators, electrocardiogram, cardiac color ultrasound, cardiac CTA, craniocerebral CT and MRI, internal and external intracranial artery evaluation, etc.;
- h) occurrence of adverse events during follow-up.

2. Data management and statistical analysis

For All the subjects who have signed the informed consent form and are qualified to be selected, all the items in the electronic medical record report form should be carefully recorded in detail, without no empty or missing items.

The investigator records the data into the electronic medical record report according to the original records and inpatient records, and the investigator ensures that the data is true and accurate.

Data that are significantly high or outside the clinical acceptance range should be verified with necessary explanation by the investigator.

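### Non-fatal extracranial bleeding, and non-fatal procedural complications other than stroke, infarction or heart failure, are in no endpoint, and like-for-like capture in both groups is not assured

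*Protocol*

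**What the plan says.** The endpoints appear twice in the Protocol, and the two lists agree. Under Study end points in section 2, the primary endpoint is "Composite end point of cardiovascular and cerebrovascular events (nonfatal ischemic stroke, Nonfatal hemorrhagic stroke, Nonfatal myocardial infarction, Nonfatal heart failure, and cardiovascular and cerebrovascular death"; the secondary list follows: "Secondary end points: cardiovascular and cerebrovascular death; All-cause death; Cardiac insufficiency; Cognitive dysfunction". Section 4, item 2 repeats it: "secondary observation endpoint: cardiovascular and cerebrovascular death; all-cause death; cardiac insufficiency; cognitive dysfunction".

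The between-group objective in section 2 is worded as benefit: "To explore the improvement of cardioembolic stroke, cardiovascular complex events, recurrent stroke and all-cause death risk, quality of life, and cardiac function".

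Of the multidisciplinary group, section 2 says: "These patients would undergo further stroke (primary/secondary) prevention intervention, as detailed in the MDT flow chart". It then lists appendage and valve surgery, catheter ablation and closure procedures, and anticoagulants as the treatments that qualify a patient as having received standard medical treatment. Patients who decline the multidisciplinary model form the routine group.

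Section 6, item 1 defines adverse events as those arising during this standard treatment, drug-related or not. Among its examples of serious events, item 3(d) names "Spontaneous bleeding: such as petechia, ecchymosis, digestive system and urinary system bleeding". The case report form in section 7.1 records surgical details (item d), adverse events in hospital (item e) and adverse events during follow-up (item h). Item f collects "general condition, vital signs, Quality of Life, HAS-BLED score, etc".

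**The concern.** The treatments listed in section 2 have foreseeable costs. The protocol recognises some of them: section 9 names spontaneous bleeding among the possible risks. The expected gain, fewer strokes and other cardiovascular events, is an endpoint compared between groups. The main expected non-fatal costs are not endpoints. A favourable composite could therefore be reported with no pre-specified harm result beside it, and a reader could not judge the net effect of the model from the listed endpoints.

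Capture is the second problem. If bleeding and complications are recorded more fully in one group than in the other, a comparison added later would not be like for like, and analysis could not repair that.

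**Working it through.** The protocol states no figure for this point, so there is none to reproduce. The check sets the endpoint lists beside the harms that the listed treatments could cause.

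| Event | In the primary composite | In a secondary endpoint | Elsewhere in the protocol |
|---|---|---|---|
| Procedure-related stroke (either type), infarction or heart failure, non-fatal | Yes | Heart failure may also count as cardiac insufficiency | Adverse event |
| Fatal bleed or fatal complication | If classed as cardiovascular or cerebrovascular | Yes, all-cause death | Adverse event |
| Non-fatal extracranial bleed, spontaneous | No | No | Named in section 6, item 3(d) |
| Non-fatal extracranial bleed, procedural | No | No | Not named; open-ended adverse-event list only |
| Other non-fatal device or surgical complication | No | No | Not named; open-ended adverse-event list only |

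The last three rows are the gap. Whether the adverse-event system closes it depends on four points.

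1. **Coverage of both groups.** Section 6 ties adverse events to this standard treatment. Section 2 says that patients with none of the listed treatments are not deemed to have received standard medical treatment. Read together, these leave it unclear whether a bleed in an untreated routine-group patient is an adverse event under the protocol.
2. **Isolation of major bleeding.** Item 3(d) puts skin petechiae beside digestive bleeding. Severity in section 6, item 4 is graded by effect on daily activities, not by any bleeding definition.
3. **The bleeding-risk score.** The score in section 7.1, item f describes risk. It is not a bleeding outcome.
4. **Comparison.** The protocol states no between-group comparison of adverse events.

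The protocol's own rationale points the same way. Section 3 cites an Asian study of closure of a high-risk patent foramen ovale and describes its main endpoint as including a haemorrhage component.

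**Could 1,200 patients inform such an endpoint?** Section 5, item 3 gives only that total. The following is an illustration on assumed rates (5% in the multidisciplinary group, 3% in the routine group) and assumed splits.

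- Formula: half-width of the 95% interval = 1.96 × √[p₁(1−p₁)/n₁ + p₂(1−p₂)/n₂].
- 600 and 600: √(0.05×0.95/600 + 0.03×0.97/600) = 0.0113, so ±2.2 points.
- 900 multidisciplinary and 300 routine: √(0.0475/900 + 0.0291/300) = 0.0122, so ±2.4 points.
- 300 multidisciplinary and 900 routine: √(0.0475/300 + 0.0291/900) = 0.0138, so ±2.7 points.

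Under these assumptions a 2-point difference would be estimated usefully but not established, since each interval includes zero. Matching could reduce the numbers analysed and widen the intervals.

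**The case against.** Four arguments stand against the point.

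**Treatment is not assigned.** The study is non-interventional, clinicians choose treatment in both groups, and every patient must meet a surgical indication. Nothing bars routine-group patients from anticoagulants or procedures. This stands against any claim that the protocol adds these treatments to one group. The expectation of more treatment rests on one sentence, "These patients would undergo further stroke (primary/secondary) prevention intervention", which gives neither its amount nor the size or direction of a bleeding difference.

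**Much harm is already counted or collected.** A reader might infer that no endpoint counts procedural harm at all. The document does not support that: procedure-related stroke, infarction, heart failure and death all enter endpoints. Nor is spontaneous bleeding a limit on what may be recorded, because the serious-event list is expressly open-ended and the general definition includes events unrelated to drugs. This narrows the gap to the last three rows of the table.

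**A safety comparison may sit in a statistical analysis plan.** A reader might also infer that these harms will go uncompared. That cannot be concluded. Adverse-event tables are commonly left to such a plan, which is not at hand. The endpoint lists also do not bound what is compared, since the objective includes quality of life, which is in neither list. What remains is that the protocol fixes the endpoints and the adverse-event definition. A later plan can tabulate adverse events but cannot make their capture equal after the fact.

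**The comparison is secondary and exploratory.** The main purpose is to set up the model and collect data. This limits the weight of the point but does not remove it, because the clinical endpoints are what the comparison will be read on.

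**Conclusion.** The point holds in a limited form. Both endpoint lists omit non-fatal extracranial bleeding and non-fatal procedural or device complications other than stroke, infarction or heart failure. The stated comparison is framed as improvement only, and equal capture of these harms in the routine group is not assured. The listed endpoints alone therefore cannot show net benefit.

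The conclusion rests on two readings: that the multidisciplinary group will on the whole receive more anticoagulation and procedures, and that the adverse-event definition may not reach routine-group patients without the listed treatments. The first is the evident intent of the text, not a fixed contrast; the second is an ambiguity, not a stated exclusion.

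The size of the harm cannot be derived, because the protocol gives no bleeding rate, complication rate or group split. The interval widths of about 2.2 to 2.7 points depend wholly on the assumed rates and splits. The point is a correctable weakness of design, not a contradiction, and confidence in it is moderate.

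**What to change.** Make three changes before the data are compared.

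1. In section 2 (Study end points) and section 4, item 2, add one secondary safety endpoint: major bleeding from any cause, spontaneous or procedural, by a named standard definition, together with procedure- or device-related complications. Count it from enrolment in both groups, through case report form items e and h.
2. Reword the adverse-event definition in section 6, item 1 so that it applies to every enrolled patient in either group, whatever treatment was received.
3. Report the safety endpoint beside the primary composite. If a combined net outcome is also shown, count each patient once, at the first event. Otherwise a procedure-related stroke or death would count both in the composite and as a complication.

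The cost is one definition, one table and slightly more careful adverse-event coding. Procedural bleeding and routine-group events need explicit instructions to the sites, so it is not quite free. The reported benefit may look less favourable. No change to treatment or to the planned number of patients is needed.

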9. Heart Rhythmology professional Committee of Chinese Medical Association, Heart Electrophysiology and Pacing Branch of Chinese Medical Association. Guidelines for the Prevention and Treatment of Cardioembolic Stroke in China (2019). *The Chinese Journal of Arrhythmia.* 2019,(06):463-484.

4. Research purpose

1. Research purpose:

Establish multidisciplinary collaboration diagnosis and treatment mode, standardize the diagnosis and treatment process: through the integration of neurosurgery, cardiac vascular surgery, neurology, cardiovascular medicine and other related disciplines, build "heart and brain treatment" multidisciplinary close cooperation system, standardize integration process and diagnosis and treatment, at the same time actively innovation relying on the relevant academic society construction, earnestly implement the multidisciplinary collaboration diagnosis and treatment mode. Based on the Internet + 5G medical model technology system and information platform, research to establish coverage relying on the remote medical service platform, the provincial, city and county center of information classification management system, by perfecting the regional collaborative emergency medical platform, improve the province cardiovascular disease acute critical patients overall treatment level, contribute to the standardization of cardiovascular stroke high-risk patients diagnosis and treatment and management. Patients with difficult and acute and critical cardiovascular and cerebrovascular diseases in the stable rehabilitation period after emergency treatment were transferred back to the primary hospital for rehabilitation, follow-up and chronic disease management and treatment.

2. Study observation endpoint

(1) Main observation endpoint: composite end point of cardiovascular and cerebrovascular events (non-fatal ischemic stroke, non-fatal hemorrhagic stroke, non-fatal myocardial infarction, non-fatal heart failure, cardiovascular and cerebrovascular death)

(2) secondary observation endpoint: cardiovascular and cerebrovascular death; all-cause death; cardiac insufficiency; cognitive dysfunction

5. Study design

1. Study site and study population

Collect high-risk patients from the Second Affiliated Hospital of Nanchang University and various hospitals of Jiangxi Province from September 2022 to September 2023.

Selection criteria: ① met the high embolic risk (including Valvular heart disease/intracardiac neoplasms, thrombosis/atrial fibrillation/infective endocarditis/PFO) in the risk stratification criteria of The Chinese Expert Consensus on Cardiac stroke Diagnosis (2020); ② meets the surgical indications for cardiac diseases related to the Chinese Expert Consensus on the Treatment of Cardioembolic Stroke (2022) (including left atrial appendicular occlusion, left atrial appendicular ligation, and atrial fibrillation radiofrequency ablation recommended for high-risk stroke patients with atrial fibrillation; Transcatheter PFO occlusion is recommended for cryptogenic stroke patients with high-risk PFO; Valve repair or replacement is recommended for patients with valvular disease. Left atrial appendage ligation or left atrial appendage clip is recommended for patients with atrial fibrillation.); ③ understood and voluntarily signed the informed consent form.

Exclusion criteria: ① with severe mental disorder and unable to express intention; ② with other abnormal signs, laboratory tests and clinical diseases, not suitable to attend investigator; ③ and unable to complete long-term follow-up.

2. Study and design flow chart:

[figure not shown]

Figure 1 Flowchart of the project

3. Sample size determination method required for the study:

This study through the real world cohort research, to cross professional association as a breakthrough point, with standardization, standardization for innovation, establish interdisciplinary diagnosis and treatment team, establish "screening-prevention-diagnosis and treatment" standardized process, for cardiac stroke high-risk patients to choose standard diagnosis and treatment basis, optimize the current diagnosis and treatment process and professional technology. It is expected that 1,200 patients at high risk of cardioembolic stroke will be included in a time period of 1-1.5 years. It should be pointed out that if compared with conventional diagnosis and treatment methods, patients matched with multiple factors in the same period are selected as the control group.

6. Safety evaluation (including the definition and evaluation of adverse events and serious adverse events)

1. Definition of adverse events: adverse medical events that occur in the course of this standard treatment of the subject, whether they are drug-related or not.
2. Abnormal laboratory and instrument examination results.
3. Serious adverse events: Major adverse events may be drug-related, including but not limited to the following:
 - (a) Abnormal laboratory indicators (including liver and kidney function, etc.);
 - (b) Allergic reaction to antiplatelet drugs / anticoagulants;
 - (c) Stroke / transient ischemic attack or neurological deficit;
 - (d) Spontaneous bleeding: such as petechia, ecchymosis, digestive system and urinary system bleeding;
 - (e) Central nervous system damage.
4. Assessment of the severity level
Light: do not affect the daily activities;
In: affect daily activities;
Heavy: loss of daily activity ability.

7. Data collection and management

1. Survey content (CRF table)

variable:

- a) Basic information of patients: name, gender, age, education level, combined diseases, past medical history, etc.;
- b) Admission status: chief complaints of symptoms, general condition, vital signs, CHA2DS2-VASc score, nutrition questionnaire and epidemiological data etc.;
- c) Pre-treatment laboratory and instrument examination: biochemical indicators, nutrient index (one carbon unit substance), electrocardiogram, dynamic electrocardiogram, cardiac color doppler ultrasound, foaming test, cardiac CTA, craniocerebral CT and MRI, internal and external intracranial artery evaluation, etc.;
- d) Treatment medication; surgical conditions
- e) The occurrence of adverse events during the hospitalization period;
- f) Situation at follow-up: chief complaint of symptoms, general condition, vital signs, Quality of Life, HAS-BLED score, etc.;
- g) Laboratory and instrumental examination at follow-up: biochemical indicators, electrocardiogram, cardiac color ultrasound, cardiac CTA, craniocerebral CT and MRI, internal and external intracranial artery evaluation, etc.;
- h) occurrence of adverse events during follow-up.

2. Data management and statistical analysis

For All the subjects who have signed the informed consent form and are qualified to be selected, all the items in the electronic medical record report form should be carefully recorded in detail, without no empty or missing items.

The investigator records the data into the electronic medical record report according to the original records and inpatient records, and the investigator ensures that the data is true and accurate.

Data that are significantly high or outside the clinical acceptance range should be verified with necessary explanation by the investigator.

The researcher will modify the data due to filling reasons, and the dialog box will pop up in the electronic medical record report form, and the researcher should indicate the reason for the modification. Any modification by the researcher leaves a mark to ensure the authenticity of the data.

After the investigator fills in the data and the supervisor monitors, the investigator solves all the data questions and ensures that the accuracy of the data is determined, the data administrator locks the database. The data management personnel, principal researchers, statistical analysts, implementers and monitoring management personnel will jointly review the data, and complete the final definition and judgment of the analysis population, and then the data manager will finally lock the database.

The locked database or files should generally not be changed again.

8. Quality Management Plan (please introduce relevant measures to ensure project quality and progress)

Surveillance of the observational cohort studies

During the study, the inspectors will regularly visit the research center to ensure that all the content of the research protocol is strictly followed, and the original data is checked to ensure that the data filling content is true, complete and correct.

1. Method of determination

(1) Brain CT and MRI;

(2) Electrocardiogram or dynamic electrocardiogram: 12-lead routine electrocardiogram; 24-hour dynamic electrocardiogram monitoring

(3) Blood routine test, urine routine test, liver and kidney function test, blood biochemical indexes: automatic biochemical analyzer;

(4) Nutrients (one carbon unit substance) : mass spectrometry or biochemistry

(5) Cardiac ultrasonography;

(6) Cardiac CTA

(7) Surgical records

(8) Combined medication

(9) Relevant scales should be applied with international common scale or Chinese version

(10) Record of adverse events.

2. Fill in the electronic case report form

Electronic case report form (CRF) was used in this trial. For All subjects who have signed the informed consent form and are qualified to be selected, all items in the electronic medical record report form should be recorded carefully and detail, with no empty or missing items. All data in the EHR report form should be checked with the original subject medical record data to ensure correct accuracy. The investigators ensure that the data are true and accurate.

3. Preservation of the original materials

The original data of this trial includes signed informed consent, release records of test products, relevant laboratory test reports, case records and other relevant records, and should be kept in the national drug clinical trial institution of the hospital where the research center is located . Medical institutions shall keep the clinical trial data until five years after the termination of the trial. The implementer shall keep the data of the clinical trial until ten years after the last produced product is put into use.

9. Pre-assessment and risk control plan of the project risk and benefits (please describe the possible risks and benefits of the researchers, the subjects and their medical institutions when conducting the project. If there are risks, please introduce the risk control measures and feasibility.)

1. Benefit / risk assessment

(1) Benefit: through the real world cohort research, to cross-professional collaboration as a breakthrough point, to diagnosis and treatment standardization, standardization for innovation, establish interdisciplinary treatment team, establish "high-risk patients with cardioembolic stroke (acute stroke) -MDT-standardized diagnosis and treatment-rehabilitation treatment" standardized process, optimize the current diagnosis and treatment process and professional technology.

(2) Possible risks:

- 1) Abnormal laboratory indicators (including liver and kidney function, etc.);
- 2) Allergic reaction to antiplatelet drugs / anticoagulants;
- 3) Stroke / transient ischemic attack or neurological deficit;
- 4) Spontaneous bleeding: such as petechia, ecchymosis, digestive system and urinary system bleeding;
- 5) Central nervous system damage.

2. Ethics and ethics

(1) Ethics Committee (should describe how the plan was approved by the Research Ethics Committee / Institutional Review Board)

- 1) Conclusion: Cardiac stroke accounts for 14% ~ 30% of ischemic stroke, and the condition is more serious, with high mortality rate, disability rate and recurrence rate. Cardiac stroke mostly has clear underlying diseases or risk factors of the cardiovascular system, including valvular heart disease, atrial fibrillation, PFO and so on. There are disciplinary barriers to prevention and treatment of cardiac stroke, standardized diagnosis and treatment process, clinical application of related surgical instruments is still in the initial stage, such as precision treatment, and need to optimize the current treatment process and professional technology, prevention and treatment of cardiac stroke, this project explores multidisciplinary collaborative treatment mode of cardiac stroke, and develops standardized diagnosis and treatment process and related professional technology.
- 2) General situation of the undertaking unit (personnel, assets, business and management status):

The second Affiliated Hospital of Nanchang University is the tertiary hospital, neurosurgery is the first neurosurgery specialty in Jiangxi Province, has become a key specialty, neurosurgery medical, teaching and research center of Nanchang University, with long-term follow-up database and specimen database, laid a solid foundation for the smooth implementation of this work. [name], the applicant of the project, was approved as the "Changjiang Scholar distinguished Professor" of the Ministry of Education, and is the "only professor" in the medical field of the province. This project sets related advantageous units and experts, covering production, learning, research, medical, inspection, use and other industries, covering research and development, production, testing, application and other links. At present, the project leader has established a scientific research team for basic BI research and stem cell intervention, whose core members have more than ten years of scientific research attainments in the fields of molecular biology, cell biology and clinical research. The personnel involved in this project all have a good training background, clinical translational research

experience, and laboratory work background, which is helpful Completed the study of this project.

3) Advantages of the participating units:

The Second Affiliated Hospital of Nanchang University of the "China Five-Star Advanced Stroke Center" won the title of "National Five-Star Advanced Stroke Center" of the Stroke Prevention and Treatment Engineering Committee of the National Health Commission in 2020. The second affiliated hospital of Nanchang university has been committed to provide efficient, high quality first aid green channel for stroke patients, formally established in 2015 stroke center, the same year approved "national senior stroke center", in 2018 in the national difficult disease (cerebrovascular disease) diagnosis and treatment promotion project (the only) in the province, the hospital established the cerebrovascular disease center, in 2018,2019,2020 consecutive "China five-star senior stroke center" title. The second Affiliated Hospital has solid technical strength and the support of the diagnosis and treatment of difficult cerebrovascular diseases. The second affiliated hospital of Nanchang university will continue to play a "China five-star senior stroke center" regional leading role, with the help of the couplet of medical, network hospital, remote consultation, nervous system difficult severe alliance platform, strengthen the training supervision, further quality medical resources sinking, at the same time to strengthen the construction of stroke prevention alliance, cultivate more stroke professional doctors, make greater contribution to stroke prevention and control, benefit more people;

In 2016, the Second Affiliated Hospital of Nanchang University took the lead in opening the "medical imaging cloud service platform", realizing the image "cloud storage" and remote film reading consultation. In 2019, with the help of cloud platform and professional operation team, the hospital established medical consortium cooperation with 111 secondary and above hospitals in the province. The telemedicine business effectively radiated to the whole province, realizing more than 100 cases of difficult diseases in a single month, and solved the problem of remote people running to see a doctor with practical measures. The remote consultation system breaks the restrictions of time, space and region, and enables high-quality medical resources to sink, so that residents in remote areas can enjoy the diagnosis and treatment of provincial medical experts without traveling hard and win valuable medical treatment time. At the same time, grassroots hospitals can also invite experts from provincial hospitals to conduct remote consultation, so as to help grassroots doctors to diagnose difficult diseases and receive support from medical technology. Each consultation process is an opportunity to receive telemedicine education and training. In the future, the construction of a comprehensive and interconnected remote platform will bring more convenient and accurate medical services to the diagnosis and treatment of difficult diseases of cardioembolic stroke.

(2) Patient information and informed consent:

This cohort study was conducted in accordance with the requirements of the current Declaration of Helsinki, medical device clinical trial regulations, GCP, and relevant national regulations.

Before the start of the study, the investigator should submit the study protocol, informed consent form and other relevant documents to the medical ethics committee of the hospital responsible for the clinical trial. Clinical trials can not be started until after obtaining ethics committee approval. Any modification to the study protocol must be approved by the ethics

committee before being implemented. Serious adverse events during the clinical trial should be promptly presented in writing to the ethics committee.

Prior to inclusion in this study, the investigator must provide the subject and his relatives with the details of the clinical trial, including the purpose of the trial, expected efficacy, possible adverse events, and countermeasures. They will be selected after the subjects fully understood the trial, accepted the informed process, and signed the informed consent.

The Informed consent was jointly signed by the study physician and the subject himself or his legal representative in duplicate, with one copy kept for each party.
